Children with Neuromuscular disease show a decline of Forced Vital Capacity (FVC), which is steeper at younger ages (13). This is especially important because the age at which FVC reaches 1 Lt and the rate of decline of FVC are variables that can predict mortality (14).

Pneumonia, respiratory exacerbations and failure are one of the most important causes of emergency admissions, hospitalisations and death in children with neuromuscular diseases and cerebral palsy (15-18). Physical health and the number of days spent outside home or hospitalised are important domains of life and predictor of Health-Related Quality of Life in children with Neuromuscular disease and children with Cerebral Palsy (19,20). In this context, it is of importance to research how to therapeutically aid airway clearance, decrease respiratory exacerbations and reduce the pulmonary function rate of decline.

Hypertonic Saline is a solution of salt water used as a nebulized medication in many conditions. Its clinical benefits include mucus clearance, microbiological diagnosis, improvement of lung function, decrease in respiratory exacerbations, cough triggering and improvement of quality of life (21). It has mucolytic and expectorant effect, reduces biofilm formation by Pseudomonas Aeruginosa and increases antioxidative thiols in the airway liquid (22).

Retrospective studies and clinical trials have shown that inhaled Hypertonic Saline is well tolerated, reduces pulmonary exacerbations, improves lung function and Lung Clearance Index, reduces absenteeism, improves Health Related Quality of Life in patients with Cystic Fibrosis independent of rhDNase treatment (23-26), and has anti-inflammatory effect in sputum decreasing

IL-8 (27). In asthmatic and healthy subjects, inhaled Hypertonic Saline have shown to enhance mucociliary clearance (28). To date, studies investigating Hypertonic Saline in bronchiectasis have produced conflicting results (29).

This study aims to assess the effectiveness of the use of nebulised Hypertonic Saline in respiratory outcomes in children and young people with Neuromuscular disease or with Cerebral Palsy.

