## Secondary Objectives:

- Assess the effect of the treatment with nebulised hypertonic saline in children and young people with Neuromuscular disease or Cerebral Palsy on the number of courses of antibiotic prescribed compared to year before starting treatment.
- Determine whether the use of nebulised Hypertonic Saline in children and young people with Neuromuscular Disease or Cerebral Palsy reduces the frequency of hospitalisations due to respiratory exacerbations compared to year before commencing treatment.
- Explore the impact of the treatment with hypertonic saline on nocturnal oxygenation and ventilation in children and young people with Neuromuscular disease or with Cerebral Palsy.
- Evaluate whether the treatment with nebulised hypertonic saline in children and young people with neuromuscular disease or cerebral palsy improves the ease of airway clearance.
- In the subgroup of participants with neuromuscular disease who can perform spirometry, assess whether the use of Hypertonic Saline decreases rate of decline of pulmonary function compared to year before commencing treatment.
- Explore how parents of children and young people with Neuromuscular disease or with Cerebral Palsy perceive the treatment with nebulised hypertonic saline compared to previous management.

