# 3. STUDY DESIGN

[Chart review of children and young people with Neuromuscular disease or with Cerebral Palsy who are cared for in the Royal Brompton Hospital and that have been treated with nebulised hypertonic saline for at least 12 months. Children and young people who are also diagnosed with Cystic Fibrosis will be excluded.

Parents or legal guardians will be asked to complete two questionnaires to further complement data from hospital records.

Participants between 10 and 18 years old will be asked to complete one questionnaire to complement hospital records.]

[Duration: 6 months.]

[We aim to review all charts of participants recruited that meet criteria between December 2011 and May 2018. We aim to recruit 40 participants from each group, including children, young people, and parents or legal guardians, as this will be a pilot study. Only participants recruited will have their charts reviewed]

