#### 3.1 STUDY OUTCOME MEASURES

**Primary Endpoints:** 

- Number of respiratory exacerbations requiring antibiotic treatment.
- Number of hospitalsiations due to respiratory exacerbations, using NHANES 2011 questionnaire for Hospitalisation and access to care HUQ.010.
- Nocturnal oximetry and polygraphy outcomes: Basal SpO2 (%), Minimum SpO2 (%), Maximum SpO2 (%), Average SpO2 (%), Oxygen desaturation index (ODI), Snoring and End tidal CO2 (EtCO2).
- Rate of decline of pulmonary function.

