# Statistical Analysis Plan:

Primary endpoint analysis:

- Univariate X analysis for categorical variables to investigate *Courses of antibiotic treatment*.
- Univariate X analysis for categorical variables to investigate *Number of hospitalisations*.
- Student t testing will be used to analyse *nocturnal oxygenation and ventilation outcomes* comparing one year before and after starting treatment with Hypertonic Saline.
- Independent t testing and Mann-Whitney U test to analyse *Rate of decline in pulmonary function*.
- Cox proportional hazard model to test differences in primary endpoints *for different baseline*

Secondary enpoint analysis:

- Univarate analysis to analyse *Ease of airway clearance*.
- Univariate analysis on **perception of treatment**.

Data and all appropriate documentation will be stored for a minimum of 10 years after the completion of the study, including the follow-up period.

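### A Cox proportional hazards model is listed for the primary endpoints, but none of them is worded as a time to an event, and the available text gives the model no event, origin or censoring rule

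*Combined protocol and SAP*

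**What the plan says.** Section 6 (Statistical Analysis Plan) has five lines under primary endpoint analysis: a chi-square analysis of antibiotic courses, a chi-square analysis of hospitalisations, a Student t test for the nocturnal outcomes, an independent t test and Mann-Whitney U test for pulmonary-function decline, and a fifth line: "Cox proportional hazard model to test differences in primary endpoints *for different baseline". The available text of that line ends without saying what follows the word baseline.

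Section 3.1 lists the primary endpoints in four bullets:
- "Number of respiratory exacerbations requiring antibiotic treatment"
- "Number of hospitalsiations due to respiratory exacerbations"
- "Nocturnal oximetry and polygraphy outcomes: Basal SpO2 (%), Minimum SpO2 (%), Maximum SpO2 (%), Average SpO2 (%), Oxygen desaturation index (ODI), Snoring", and end-tidal CO2
- "Rate of decline of pulmonary function"

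The outcome list in the Study Summary repeats these. The secondary objectives in section 2 set antibiotic courses, hospitalisations and lung function against the year before treatment. For antibiotics, for example, the effect is assessed "on the number of courses of antibiotic prescribed compared to year before starting treatment".

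**The concern.** A Cox model takes as its outcome the time from a defined origin to a defined event, with a rule for when observation stops. The line applies it to the primary endpoints collectively, and those are counts, measurements and a slope. An analyst following the text could not fit the model to most of the listed endpoints. For the two counts, the analyst would first have to choose what is timed, from when and until when.

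What is at stake is limited. The line appears to be the plan's only method for asking whether results differ by baseline factors. If it cannot be carried out as written, that question has no usable pre-specified method, and different analysts could reasonably construct different outcomes. The other four primary analysis lines do not depend on it.

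**Working it through.** No published figure has to be reproduced: the plan gives no hazard ratio, event number, alpha or power for this model. The check is a comparison of texts.

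**Step 1: classify the primary endpoints in section 3.1.**

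| Bullet | Variables | Type | Time to event? |
|---|---|---|---|
| Exacerbations needing antibiotics | 1 | Count | No |
| Respiratory hospitalisations | 1 | Count | No |
| Nocturnal oximetry/polygraphy | 7 (basal, minimum, maximum and average SpO2, ODI, snoring, end-tidal CO2) | Measurements, an event rate (ODI), and snoring with no stated scale | No |
| Pulmonary-function decline | 1 | Slope | No |

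Total: 1 + 1 + 7 + 1 = 10 variables. Time-to-event: 0 of 4 bullets, 0 of 10 variables.

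**Step 2: look for the missing elements elsewhere.**
- *Event.* The only timed milestone is in section 1.1, which says that "the age at which FVC reaches 1 Lt and the rate of decline of FVC are variables that can predict mortality". This is background and is not listed as an endpoint.
- *Origin.* The start of hypertonic saline anchors the before/after comparison, but it is not assigned to the Cox model. It could not be time zero for the year before treatment.
- *Censoring.* Section 3 gives a chart window: "We aim to review all charts of participants recruited that meet criteria between December 2011 and May 2018". It is not named as a censoring date. The withdrawal section (4.4) and the assessment and follow-up section are marked as not applicable.

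**Step 3: could the endpoints be recast?** For the two counts, yes: time to first event, or recurrent dated events. Section 4.2 requires at least 12 months on treatment, so the first treatment year has passed for every eligible child and there would be little or no censoring in it. For the other eight variables (7 + 1), the plan defines no event and no evident recasting keeps the endpoint as stated.

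**Step 4: what precision could a replacement offer?** This bears on the cost of the fix, not on the defect. Take the ratio of after/before rate ratios between two diagnosis groups, equal 12-month periods, simple Poisson counts and an assumed mean of m = 1 event per child per year in each period:

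SE(log ratio) = sqrt(2/(nA × m) + 2/(nB × m)); 95% CI = estimate multiplied and divided by exp(1.96 × SE).

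| Children per group | SE | CI factor |
|---|---|---|
| 40 + 40 | sqrt(0.050 + 0.050) = 0.316 | 1.86 |
| 20 + 20 | sqrt(0.100 + 0.100) = 0.447 | 2.40 |
| 30 + 10 | sqrt(0.067 + 0.200) = 0.516 | 2.75 |

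The last two rows cover the reading of sections 3 and 6 in which 40 is the total number of children. The event rate and the splits are assumptions; the documents give none. Overdispersion would make the factors larger.

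**The case against.** The strongest objection is that the line is visibly incomplete. Words lost when the PDF was read are not missing from the plan, and a continuation might name an event, for instance time to first admission. That stands as a limit: the absence of an event, origin and censoring rule can be asserted only for the available text. It does not reach the mismatch of type, because the outcome is named before the break and no continuation turns SpO2 values or a slope into event times.

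Second, a reader might infer that a Cox model is impossible for every primary endpoint. The documents do not support that. A recurrent-event Cox model works on dated events, and those events could be the ones being counted. For the two counts the line is underspecified rather than unworkable.

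Third, a reader might infer that the outcome would have to be made up with the data in view. The charts exist already, so that is possible, but nothing in the documents excludes fixing the outcome before extraction. All that is shown is that it is not fixed in the available text.

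Finally, this is an exploratory pilot and the line is supplementary. That limits the consequence. It does not make the model fit the endpoints.

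**Conclusion.** The point holds in a limited form. The plan lists a model that does not fit the endpoints it names: 0 of 10 primary variables is worded as a time to an event, eight do not fit a Cox model as defined, and two could be used only after a recasting that the available text does not make. One of five primary analysis lines is affected.

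A reader might also infer that the before/after results are distorted. They would not be: the other four lines stand apart from this one, and no numerical effect is claimed.

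The finding of mismatch rests on the endpoint wording alone. The description of the line as a baseline-factor analysis is an inference from its last word. The line should be corrected, but it does not undermine the study.

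**What to change.** Delete the Cox line. If no baseline-factor analysis is needed, that alone cures the defect.

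If one is wanted, replace the line with a pre-specified exploratory analysis of a few named factors already in the chart, for example diagnosis group and age at start. Use models that match each endpoint and account for the two periods within a child, and report estimates with confidence intervals:
- **Antibiotic courses and hospitalisations:** Poisson or negative-binomial model over the 12 months before and after starting, with an offset only where a child's observed period is shorter.
- **Continuous nocturnal measures:** linear mixed model, with a suitable alternative for bounded or rate measures such as maximum SpO2 and ODI, and a binary or ordinal model for snoring if it is recorded that way.
- **Pulmonary-function decline:** linear mixed model in the neuromuscular subgroup named in section 2, without a diagnosis-group interaction.

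Alternatively, keep Cox for the two event endpoints only, with event, origin and censoring defined before analysis.

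The cost is a change of wording and a little more analysis work. The Cox route needs event dates; placing charted events in the year before or after starting already requires them, but the parent questionnaire collects only numbers. The downside of the replacement is imprecise interaction estimates, as the factors above show, so it should be labelled exploratory.

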## 7. REGULATORY ISSUES

#### 7.1 ETHICS APPROVAL

The Study Coordination Centre has obtained approval from the Yorkshire & The Humber - Leeds West Research Ethics Committee (REC) and Health Regulator Authority (HRA). The study must also receive confirmation of capacity and capability from each participating NHS Trust before accepting participants into the study or any research activity is carried out. The study will be conducted in accordance with the recommendations for physicians involved in research on human subjects adopted by the 18th World Medical Assembly, Helsinki 1964 and later revisions.

#### 7.2 CONSENT

Consent to enter the study must be sought from each participant only after a full explanation has been given, an information leaflet offered, and time allowed for consideration. Signed participant consent should be obtained. The right of the participant to refuse to participate without giving reasons must be respected. After the participant has entered the study the clinician remains free to give alternative treatment to that specified in the protocol at any stage if he/she feels it is in the participant's best interest, but the reasons for doing so should be recorded. In these cases, the participants remain within the study for the purposes of follow-up and data analysis. All participants are free to withdraw at any time from the protocol treatment without giving reasons and without prejudicing further treatment.

# 7.3 CONFIDENTIALITY

The Chief Investigator will preserve the confidentiality of participants taking part in the study and is registered under the Data Protection Act.

#### 7.4 INDEMNITY

Imperial College London holds negligent harm and non-negligent harm insurance policies which apply to this study.

#### 7.5 SPONSOR

Imperial College London will act as the main Sponsor for this study. Delegated responsibilities will be assigned to the NHS trusts taking part in this study.

#### 7.6 FUNDING

This section does not apply.

#### 7.7 AUDITS

The study may be subject to inspection and audit by Imperial College London under their remit as sponsor and other regulatory bodies to ensure adherence to GCP and the NHS Research Governance Framework for Health and Social Care (2nd edition).

## 8. STUDY MANAGEMENT

The day-to-day management of the study will be co-ordinated through [name].

## 9. PUBLICATION POLICY

[ Data ownership rights will lie with the institution. Findings of this study will be presented as a Dissertation and will be available through Open Access. We aim to publish findings in peer-review journals. [name] will take the lead in the publication and dissemination.]

#### **APPENDICES**

- **Appendix 1** Questionnaire on Hypertonic Saline treatment for parents and legal guardians.
- **Appendix 2** Questionnaire on Hypertonic Saline treatment for participants 16 18 years.
- **Appendix 3** Questionnaire on Hypertonic Saline treatment for participants 10 15 years.
- Appendix 4 Consent form
- Appendix 5 Consent form
- Appendix 6 Assent form

# Hypertonic saline treatment questionnaire PARENTS/LEGAL GUARDIAN

Participant II	D:								Date:	/	/
1)Overall, d had has bee		eel th	at neb	ulised	hypert	onic sa	line yo	ur child	l / your	ng perso	n has
	ul useful n't know	,									
What have yo	u found	most (	useful a	bout it?	•						
What have yo	u found	most o	difficult,	/ trouble	esome a	bout it?					
2)Please sco airway Before startin				ink it l	nas bee	n to cle	ear spu	tum fro	om your	child's	
0	1	2	3	4	5	6	7	8	9	10	
	+	+	$\dashv$	+	$\dashv$	+	$\dashv$	+	+	$\dashv$	
Most Easy		 							· • •	► Most D	ifficult
After starting	Hyperto	nic Sal	ine								
0	1	2	3	4	5	6	7	8	9	10	
1	1	1	- 1	- 1	- 1	- 1	- 1	- 1	- 1	1	
	$\top$	$\top$								$\dashv$	
Most Fasy										Most D	ifficult

Participant ID:		Date:/
In the 12 months before starting did your child need? If you don't		
Oral		
IV		
In the 12 months after starting H your child need? If you don't rem	· · · · · · · · · · · · · · · · · · ·	urses of antibiotics did
Oral		
IV		
In the 12 months before starting take your child to see a doctor be don't remember, please leave it b	ecause s/he was unwell with a	
In the 12 months after starting take your child to be seen by a do If you don't remember, please lea	octor because s/he was unwell	

# Hypertonic saline questionnaire

[figure not shown]
Ages 16 to 18 years

Participant ID:	Date:	_/	_/
1)Overall, do you feel that nebulised hypertonic saline has been			
Useful Not useful I don't know			
What have you found most useful about it?			

[figure not shown]
What have you found most difficult/ troublesome about it?

# 2)Please score your perception of how easy it is to clear sputum.

Before starting Hypertonic Saline

After starting Hypertonic Saline

[figure not shown]

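### The clearance score after starting saline has no reference period on any of the three forms, so respondents may rate different stages of treatment and the change score mixes saline with a varying amount of disease course

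*Combined protocol and SAP*

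**What the plan says.** Appendices 1 to 3 each ask for two clearance scores. On the form for ages 16 to 18 the stem is "Please score your perception of how easy it is to clear sputum" and the two scales are labelled "Before starting Hypertonic Saline" and "After starting Hypertonic Saline". The form for ages 10 to 15 has the same two labels and also a present-tense stem. The parent form labels its second scale in the same way, but its stem asks how easy clearance has been. The scale graphics on the child forms are not visible in the text and the parent stem is partly garbled, but the labels for the score after starting are complete and carry no period.

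Further down the parent form, the antibiotic and doctor-visit items do carry one: "In the 12 months before starting" and "In the 12 months after starting".

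Section 4.2 requires a minimum of 12 months on nebulised saline and gives no upper limit. Section 3 covers charts of participants who meet the criteria "between December 2011 and May 2018". In Section 2, the antibiotic, hospitalisation and spirometry objectives name the year before treatment as comparator, while the clearance objective names no period. In the Statistical Analysis Plan (Section 6), the nocturnal outcomes are compared one year before and after starting. Clearance gets one line announcing a univariate analysis, with no period and no adjustment for time on saline.

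**The concern.** Ease of clearance is a secondary endpoint (Section 3.1), but it is also the second of the two aims in the Study Summary. There is no control group, so the difference between the two scores is the planned quantitative evidence on that aim.

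Section 1.1 says that vital capacity falls as neuromuscular disease progresses, links low inspired volume and weak expiration to impaired cough, and reports a decline in FVC that is steeper at younger ages. If one family rates the months just after starting and another rates the present several years on, the two change scores describe different things, and the later one contains more disease course and growth. The mean change would then depend partly on when children happened to start and on how each respondent read the question.

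This cannot be repaired at analysis. The chart can show how long a child has been on saline, but not which part of that time the respondent had in mind.

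**Working it through.** The plan gives no figure of its own for this point. The check is date arithmetic plus a comparison of the items.

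**Inputs**
- Minimum time on saline: 12 months; no maximum (Section 4.2).
- Chart window: December 2011 to May 2018 (Section 3).
- Study duration: 6 months (Section 3).

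**Time on saline when the form is completed**
- Length of window: (2018 − 2011) × 12 + (5 − 12) = 84 − 7 = 77 months; 77 / 12 = 6.4 years.
- Shortest time on saline: 12 months = 1.0 year.
- Longest, if the 12 months before starting must also lie inside the window: 77 − 12 = 65 months; 65 / 12 = 5.4 years.
- Longest, if saline could start in December 2011: 77 months = 6.4 years.
- If forms are completed up to 6 months after May 2018: 65 + 6 = 71 months (5.9 years) and 77 + 6 = 83 months (6.9 years).

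The upper limits assume that saline started inside the window. Section 3 does not say so, and no distribution of start dates is given.

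**Period named for each before-after outcome**

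| Outcome | Period before starting | Period after starting |
|---|---|---|
| Antibiotic courses, parent form | 12 months | 12 months |
| Doctor visits, parent form | 12 months | 12 months |
| Nocturnal outcomes, SAP | one year | one year |
| Hospitalisations, Section 2 | one year | not named |
| Spirometry decline, Section 2 | one year | not named |
| Clearance score, all forms and SAP | not named | not named |

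Clearance is the only outcome in the table with no period on either side.

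**Readings open to a respondent**
1. The first weeks on saline.
2. The whole time since starting, which suits the parent stem.
3. The present, which suits the present-tense stem on the child forms. That stem also covers the score before starting, so it is a weak guide.

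Under reading 3, the rating falls anywhere from 1 to 5.4 (or 6.4) years after starting. Under reading 2, it averages over a period of that varying length. Only under reading 1 do respondents refer to the same stage of treatment.

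**The case against.** **The range is not the period rated.** A reader might infer that the score itself describes a point between 1 and more than 5 years on saline. The documents do not support that. The range is time on saline at completion, its top end rests on an assumed start inside the window, and long-term users may be few. This stands, and the range is used here only in that sense.

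**The size is unknown.** A reader might also attach a bias in points. For example, with an assumed worsening of 0.1 to 0.3 points a year on the 0–10 scale, the shift would be 0.1 to 0.3 points at 1 year, and at 5.4 years 0.1 × 5.4 = 0.5 to 0.3 × 5.4 = 1.6 points. The documents give no rate for perceived clearance and no progression rate for cerebral palsy. An FVC decline that is steeper at younger ages also argues against a constant yearly drift. Both scores are given on one form, so their difference is a perceived contrast and not two dated measurements. This stands: no size can be claimed.

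**Rewording the child forms could do harm.** The present-tense item may be the one rating that needs little recall. A 10-year-old with 5.4 years on saline would have to rate a year that began at about age 10 − 5.4 = 4.6. The child forms show no 12-month items, so the argument that such recall is already asked for covers parents only. This stands and shapes the fix.

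**A 12-month window does not separate saline from disease course.** True: an uncontrolled comparison mixes them at 12 months too. The window makes the amount more uniform; it does not remove it.

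What remains is that the period is undefined on every form and the analysis ignores time on saline.

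**Conclusion.** The point holds as a gap in definition. No form, objective or analysis line says which period the score after starting refers to, while time on saline at completion can differ from 1 year to about 5.4 or 6.4 years, given a start within the chart window. Respondents can fill the gap differently, and in progressive disease the change score then mixes saline with a varying amount of disease course. The argument from disease course is firmest for neuromuscular disease. For cerebral palsy, Section 1.1 describes aspiration and developing lung disease but gives no rate.

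The documents do not establish how large the distortion is, and they do not show that a benefit would be hidden or reversed. For a secondary endpoint in a pilot this is a cheap improvement rather than a threat to the whole study. The lack of definition itself needs no assumption about drift.

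**What to change.** 1. **Parent form.** Word both clearance items with the windows the form already uses: "In the 12 months before starting" and "In the 12 months after starting" saline.
2. **Child forms.** Keep the present-tense rating after starting, state in the SAP that it is current state at completion, and do not impose a 12-month recall. Parent and child scores then describe different periods, so analyse them separately.
3. **Time on saline.** Compute months on saline as form date minus start date from the chart, and report its distribution. In a sensitivity analysis fit change = a + b × (months − 12). The intercept a is the estimated change at 12 months; report it with its confidence interval. For the child forms, b reflects time on saline together with age, disease course and recall of the state before starting. For the reworded parent items, it mainly reflects how far back the parent is recalling.

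**Cost.** A wording change on one form, one definition in the SAP, a start date from charts already under review, and one extra covariate in a small pilot. Because 12 months is the lower edge of the data, the interval there may be wide. Parents of early starters must recall a more distant year, which the form already asks of them for antibiotics and doctor visits. Confounding with disease course remains and should be stated as a limitation.
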